## 4.2. Intervention

The planned intervention is the delivery of a standardised series of group-based workshops amongst a cohort of NHS nurses that consent to participate. The workshops will provide these study participants with an understanding of the Chimp Paradox Model (CPM) and help facilitate them in acquiring the skills required to apply the model to themselves in their world. All groups will be delivered at a meeting room based in the NHS to minimise travel time for participants. If there are any obstacles that prevent participants from accessing the groups in person (such as health problems, policy changes, transportation problems, etc.), these will be facilitated online using video-conference technology in a way that preserves the participatory nature of the intervention.

The workshop series will consist of eight, ninety-minute interactive sessions, one week apart. Each standardised workshop will be delivered and facilitated by a member of the Chimp Management team. Each workshop will be structured and delivered using a standardised presentation describing the principles of the model within that session. At specified stages of the presentation, participants will be encouraged to engage in facilitated small group discussions consisting of 6-8 people.

In addition to attendance at the workshops, study participants will all be given a copy of The Chimp Paradox book as a reference source. They will be requested to read particular chapters between the sessions and asked to spend some time contemplating key areas covered that week. This is to allow for continuous learning; specifically, the development of insight, acquisition of skills and application of these skills to themselves. Sessions 1-4 will introduce the basic principles of the CPM and sessions 5-8 will cover: communication, success, happiness and leadership.

## 4.3. Measures

### *Primary outcome measure*

Occupational burnout will be measured using the Oldenburg Burnout Inventory (OLBI), a 16-item questionnaire designed to assess two facets of burnout, emotional exhaustion (OLBI-E) and disengagement (OLBI-D), including their cognitive and somatic aspects (Demerouti, Bakker, Nachreiner, & Schaufeli, 2001). For both dimensions, four items are phrased positively and four items are phrased negatively (reverse scored). Every item is scored between 1 (strongly agree) and 4 (strongly disagree), and item ratings are averaged into a single index (range = 1 to 4), where a higher score is indicative of increased burnout. Examples of positively and negatively phrased items are: "I can tolerate the pressure of my work very well"; "During my work, I often feel emotionally drained". A psychometric validation study applying the OLBI in 2599 adults with a variety of professional backgrounds demonstrated high internal consistency (Cronbach's alpha = .74 to .76 for each subscale) as well as robust convergent, and discriminant validity (Halbesleben & Demerouti, 2005).

### *Secondary measures*

The Warwick-Edinburgh Mental Well-being Scale (WEMWBS) is a 14-item questionnaire; each answered on a 1 to 5 Likert scale. Items cover different aspects of eudaimonic and hedonic mental wellbeing and are worded positively. Item scores are summed to produce a total score (range: 14 to 70), where higher scores indicate greater psychological well-being. Psychometric testing has indicated that this measure was valid, reliable and acceptable measure of well-being in adult respondents (Tennant et al., 2007); with good internal consistency (Cronbach's alpha = .89 to .91) and test-retest reliability (.81).

Participants will be asked to report the number of sickness absence days they have had during the 6-month period preceding the start of the study, and will self-report any sickness absence days taken during the active study and observation period.

Participants will also be asked to report basic demographics (age, gender, ethnicity) and generic information about their work setting (adult services, children's services, inpatient vs. outpatient care).

#### 4.4. Recruitment, study procedures and data collection

##### *Participant recruitment process*

- The RDaSH NHS Trust research team will promote the study using usual channels of communication with staff: newsletter circulated via email from the NHS communications team, via the staff intranet front page, and via posters placed in communal areas (i.e. cafeterias, meeting rooms, hospital corridors). A standard promotional leaflet will be promoted through these methods (see Appendix).
- Potentially eligible participants will receive copies of the study information sheet in three ways: (1) via email from the research team; (2) printed copies distributed to the team base and placed in staff inboxes; (3) printed copies distributed by a clinical studies officer at local team meetings.
- Potential participants will have the opportunity to contact the research team to clarify questions, if necessary, prior to the deadline for providing consent to participate (within 2 weeks). They will be asked to provide consent electronically using an online consent form which will be accessible through a weblink embedded in the information sheet. This method will ensure that no paper copies can be lost or misplaced in the post, and will be an efficient way to gather informed consent using an industry-standard and secure survey system (Qualtrics). An sample text for the consent form that will be available electronically is provided in the Appendix. The promotional material will clearly indicate the deadline for application to participate. NHS managers and/or team leaders will not be involved in the consenting process, which will minimise administrative burden and the potential for selection biases or the application of undue pressure on potential participants.
- Consenting participants will be randomly allocated to the immediate intervention group (group 1), or the waitlist control (delayed intervention) group. Allocation will be carried out by the research team, using a computerized randomization schedule, and will be communicated directly to study participants via email within a week of the application to participate deadline.
- The research team based at RDaSH NHS Trust will inform the CPM intervention facilitators when their recruitment target has been met, providing a list of consenting participants after the randomisation process has been concluded. This will ensure CPM facilitators will know how many participants to expect in each of the intervention groups. A research assistant linked to the RDaSH research team will work closely with the CPM intervention facilitators to coordinate the organisation of the groups.

##### *Organisation of the intervention groups*

- Participants will attend the sessions which will take place at St Catherine's House in Doncaster on the site of the RDaSH Trust Headquarters. To allow flexibility, staff will have the opportunity to attend one of the groups (n=4 groups running simultaneously) which occur throughout the week. Sessions will be held on a Tuesday lunchtime and Tuesday evening and Thursday lunchtime and Thursday evening. Details of the sessions, including exact location, dates and times will be provided via email to the consenting participants by email following the outcome of the randomisation process. Staff can attend any one of the sessions as long as they complete one session per week. We expect that those who agree to take part in the trial complete one session for each of the 8 consecutive weeks, however we understand that some will be unable to do so, therefore we will consider a participant as having dropped out of the trial if they miss four or more sessions.
- After the Group 1 have completed the eight-week intervention, the second group will attend the sessions and complete the same intervention using the process outlined above.

##### *Data collection and safeguarding procedures*

- All participants irrespective of group allocation will be asked to complete the primary and secondary measures described above, at four assessment points, as illustrated in Figure 1 (weeks 0, 8, 16, 40). The measures will be gathered by an independent researcher, who is not involved in the intervention. The researcher will use a secure, web-based, data collection system called Qualtrics.

Therefore, all data collection will be in electronic form, using unique participant pseudonyms, which cannot personally identify any of the study participants, or identify their random allocation.

- At the time of attendance at their initial group intervention session, participants will be asked to complete a brief checklist where they will report basic demographics and generic information about their role (see Appendix 3). These paper-based surveys will be entirely anonymous (no names, pseudonyms or identifiers), in order to protect participants' confidentiality. Participants will be asked to deposit their survey into a box, which will be managed by a member of the research team, who will then transcribe the results onto a spreadsheet, which will be safely stored in a secure network drive. The only reason to collect these data is to enable the research team to provide basic aggregated sample characteristics (e.g., mean age and standard deviation, % of people from a minority ethnic group, etc.) This will enable us to assess if the study sample is broadly representative of the wider NHS workforce or not.
- The dataset will be stored in a secure University network drive, only accessible to members of the research team, which is located behind The University of Sheffield Firewall. This will ensure the security and adequate storage of research data, consistent with NHS and academic codes of information governance and data protection.
- All analyses will be carried out at a University site, and data will be held in a restricted-access drive. The study dataset will be held at the University for a minimum of 5 years after the conclusion of the study.
- Participants will be contacted by email two weeks after randomisation has been completed to request that they complete an anonymised electronic survey gathering basic information for descriptive purposes (e.g., role, age, gender, years/months of experience, qualifications, etc.). As described above, all survey-based information will be securely stored using fully pseudonymised data files located in a password protected network drive at the University of Sheffield, only accessible to members of the research team.

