##### *Inclusion criteria*

- The study participants will be nursing staff currently working in Rotherham Doncaster and South Humber NHS Foundation Trust (RDaSH), either full-time or part-time.
- All participants will be RDaSH employees and hold an active professional registration with the Nursing and Midwifery Council (NMC).
- aged 18+

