##### *Exclusion criteria*

- Currently accessing or referred to any concurrent psychological intervention delivered by a professional.
- Nurses that are currently not in active service at the time of recruitment (e.g., on sick leave, maternity leave or suspended for any reason).

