### 5.3. Secondary analyses

ANCOVA (and sensitivity analyses) described above will be repeated at each of the time-points illustrated in Figure 1 (weeks 0, 8, 16, 40), using the OLBI (total score; then separate domain scores), and using the WEMWBS as an outcome, controlling for baseline scores. Outcomes at 6-months follow-up (pooled for both groups) will be compared to outcomes at the baseline assessment, using paired-samples t-tests (or an appropriate non-parametric test depending on the distribution of the data).

We will carry out an exploratory analysis of sickness absence, by comparing the mean number of sickness absence days reported by all participants for the 6 months preceding the start of the study, and the mean sickness absence days reported during the 6-month follow-up period after both groups completed the intervention. This within-group comparison will be carried out using a paired-samples t-test (or an appropriate non-parametric test depending on the distribution of the data).

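### Service status is checked only at recruitment, so the before-after comparison of raw sickness days has no time-at-risk denominator and the week-40 OLBI may mix ratings of different jobs

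*Protocol*

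**What the plan says.** Section 4.1 (Inclusion criteria) admits "nursing staff currently working in Rotherham Doncaster and South Humber NHS Foundation Trust (RDaSH), either full-time or part-time". The exclusion criteria remove "Nurses that are currently not in active service at the time of recruitment", with sick leave, maternity leave and suspension as examples. Both conditions are tied to entry, and the protocol describes no later check.

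Section 4.4 (Data collection and safeguarding procedures) then states: "All participants irrespective of group allocation will be asked to complete the primary and secondary measures described above, at four assessment points". These points are weeks 0, 8, 16 and 40. The primary outcome, the OLBI, is worded around the respondent's work; a sample item in section 4.3 is "During my work, I often feel emotionally drained". For absence, participants report days for the 6 months before the study and "will self-report any sickness absence days taken during the active study and observation period".

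The other data described are demographics, type of work setting, role, experience and qualifications. The paper checklist at the first session carries no identifier. The descriptive electronic survey goes out once, two weeks after randomisation. Dropout is defined by missed sessions, not by leaving employment.

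Section 5.3 uses the follow-up data in two pooled comparisons without a concurrent untreated group. For the scales, "Outcomes at 6-months follow-up (pooled for both groups) will be compared to outcomes at the baseline assessment". For absence, which is labelled exploratory, pre-study mean days are compared with "the mean sickness absence days reported during the 6-month follow-up period after both groups completed the intervention". Section 5.2 imputes missing data by an expectation-maximization algorithm and makes no exception for nurses who have left.

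**The concern.** A count of sickness days can be interpreted only against the time during which a day could have been recorded. A nurse who resigned, or went on maternity leave, part-way through weeks 16-40 has less such time, yet her low or zero count enters the mean as if she had been exposed throughout. The planned comparison has no denominator to correct this.

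The OLBI has a related problem. A nurse who has moved rates a different job, and one who is on leave rates work she is not doing. At week 40 those scores are pooled with scores from nurses still in the post in which they were recruited.

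Section 2 itself links burnout to absenteeism and staff turnover, so time out of service may well be related to the outcome. What is at stake is a listed secondary objective (sickness absence) and the reading of Hypothesis C (lower burnout at follow-up than at baseline). A statistical analysis plan cannot correct for a status that was not collected, so the item has to be in the surveys before data collection starts.

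**Working it through.** **Inputs from the protocol.** Assessments at weeks 0, 8, 16 and 40, so the follow-up window is weeks 16-40 (24 weeks). Analysable sample 2 × 67 = 134; recruitment target 134/0.70 = 191.4, rounded up to 192, as section 5.1 states. The point disputes neither figure; they serve only as n below.

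**Assumptions (no figures in the protocol).** A share p of 5-15% leaves the Trust post, evenly over weeks 0-40, and reports no sickness days after leaving. True intervention effect zero.

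**Step 1: time at risk lost in the follow-up window.** Of the leavers, 16/40 go before week 16 and lose the whole window; 24/40 go within it and lose half on average.

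Loss = p × (16/40 × 1 + 24/40 × 0.5) = p × (0.4 + 0.3) = 0.7p

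| p | loss in mean follow-up days |
|---|---|
| 5% | 3.5% |
| 10% | 7.0% |
| 15% | 10.5% |

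**Step 2: the pre-study window.** Active service is required only at recruitment, so some participants will have started, or returned from leave, during the preceding 6 months. If a share q did so evenly over that window and reports no days from before, they lose half of it on average: loss = 0.5q, i.e. 2.5%, 5.0% and 7.5% for q = 5%, 10% and 15%. The two losses cancel when 0.5q = 0.7p, that is q = 1.4p. With q = p = 10% the apparent fall is 1 − 0.93/0.95 = 2.1%. With q above 1.4p the artefact looks like an increase. Neither p nor q can be read from the data described.

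**Step 3: effect on the absence test.** SE = SD × √(2(1−r)/n) and P(significant reduction) = Φ(bias/SE − 1.96), with a nominal value of 2.5%. Take an assumed mean of 8 days, SD 15, r = 0.5, n = 134, p = 10% and no pre-study loss. Bias = 0.07 × 8 = 0.56 days; SE = 15 × √(1/134) = 1.30; P = Φ(0.43 − 1.96) = Φ(−1.53) = 6.3%. Over mean/SD of 5/12 or 8/15, r of 0.2-0.5, n of 134-192, shares of 5-15%, and between half and all of the window lost by those nurses, P runs from about 3% to 20%.

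**Step 4: OLBI at week 40.** If a share p of respondents is out of post and scores D standard deviations differently, the pooled mean moves by p × D. With p = 10% and |D| = 1 that is 0.10 SD. The protocol gives neither the size nor the sign of D. Taking D as a fall, n = 134 and r = 0.5: SE = √(1/134) = 0.086 SD, and P = Φ(0.10/0.086 − 1.96), about 21%. With a fall of 0.5 SD it is about 8%. If D is a rise, the same artefact hides improvement.

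**Step 5: the primary analysis.** The week-8 ANCOVA compares randomised groups. Equal shares out of service in both groups leave the comparison unbiased, and only 8 weeks have passed in which anyone could leave.

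**The case against.** The strongest objection is that a reader might infer much more than the documents support: that nurses who leave will look less burnt out and less often sick, so that both week-40 claims would succeed with no effect. Four points count against that reading.

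- **Direction.** No section says that leavers or nurses on leave score lower on the OLBI. Nurses on sick leave in follow-up add absence days, and excluding those on sick leave at entry also pushes towards apparent worsening.
- **Hypothesis C has two limbs.** Week 40 must be below baseline and also not differ significantly from end of treatment. In a simulation with p = 5-15%, an assumed fall of 0.5-1.0 SD in those out of post, r = 0.6 between all time points, 30% of leavers gone by end of treatment and no effect, the baseline limb alone was falsely met in roughly 6-58% of trials. Both limbs were met in roughly 4-30%.
- **Non-response.** Those rates assume that every leaver answers. A leaver who does not respond would have a score imputed, and imputation from responders would not create the assumed fall.
- **Not strictly unrecorded.** Sick leave is partly captured by self-reported sickness days. The survey forms in the appendices are not available here, so a status item there cannot be excluded.

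It is also fair to say that these comparisons are secondary or exploratory, and that the missing concurrent control is their larger weakness. Recording service status would not make them causal.

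What stands is narrower. Leavers, maternity leave, other leave and suspension are recorded by no item the protocol describes, and section 5.3 uses raw days with no denominator. Uncertainty about direction is a reason to collect the status, not a reason to ignore it.

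**Conclusion.** The point holds for the exploratory absence comparison and, more weakly, for the week-40 OLBI. As described, the absence comparison is biased by time not at risk: about 3.5-10.5% of mean follow-up days if 5-15% leave evenly and report none afterwards, offset or reversed by whatever time is missing from the pre-study window. The net direction is uncertain. For the OLBI, ratings of another job or none may enter the pooled score, but neither size nor sign can be derived from the protocol, and the false-positive rates above depend wholly on the assumed fall. The documents do not support saying that the week-40 results would be spuriously favourable. The randomised week-8 test is little affected and needs no change. All shares, shifts, means, SDs and correlations are assumptions.

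**What to change.** **Data collection.** Add one item, under the study pseudonym, to the week 0, 8, 16 and 40 surveys. It should ask for current service status; the date of leaving or changing post; and the dates or number of days not in service for reasons other than sickness (not employed in the Trust post, maternity or other leave, suspended). The recall period is since the last survey, or at week 0 the preceding 6 months. The week-0 part is essential, because without it half of the absence comparison still has no denominator. Asking for days or dates, not just a tick for today's status, captures leave that starts and ends between surveys, in particular within weeks 16-40.

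**Section 5.3.**
- Compare sickness absence as days per day in service in both windows.
- Report service status by group at each time point.
- Report week-40 OLBI in nurses still in post as a descriptive sensitivity analysis only. It should not be a condition for the claim, because restricting to stayers selects on something related to the outcome. If leaving rises with week-40 burnout (assumed log-odds 1 per SD, r = 0.6) and 5-15% leave, stayers show a spurious fall of about 0.02-0.05 SD with no effect.

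The week-8 intention-to-treat ANCOVA keeps all randomised nurses as planned.

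**Cost.** A slightly longer survey at four time points, a few sentences in section 5.3 and a little more analysis.

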## 5. Data analysis

### 5.1. Sample size calculation

A sample size calculation was performed using the method described by Cohen (1992). There is no precedent for this type of trial in this setting, so it is not known whether exposure to the CPM intervention may be associated with small, moderate or large effects on measures of occupational burnout or well-being. We have therefore followed conventional sample size calculation methods described by Cohen (1992), expecting a moderate effect size as a conservative assumption. In order to detect a moderate effect size using between-groups ANCOVA, with 80% power, and an alpha level of 0.05, and controlling for intake severity, we estimate that at least 67 participants are needed per group. This would yield a minimum sample size of 134. Expecting a 30% dropout rate, which is common in studies of psychological interventions, we would need to inflate the recruitment target to 192.

### 5.2. Primary analysis

Trial data will be summarised using a CONSORT diagram and all analyses will be based on *intention-to-treat* principles. Missing data will be imputed using an expectation-maximization algorithm, prior to conducting formal analyses.

The primary hypothesis test (A) will be based on comparing mean outcome measures between groups at week 8, as shown in Figure 1. Mean OLBI scores will be compared between groups using analysis of covariance (ANCOVA), controlling for baseline severity.

Sensitivity analyses will be performed to assess the robustness of the main findings. This will involve repeating the comparison of means whilst controlling for any potential site-effects (systematic differences in burnout between NHS services), introducing a site variable as a random effect.

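### EM imputation followed by an ordinary ANCOVA carries no imputation uncertainty forward: the week-8 test either understates its standard error or, if group is left out of the EM model, shrinks the treatment effect

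*Protocol*

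**What the plan says.** Protocol section 5.2 sets the order of work. First, "Missing data will be imputed using an expectation-maximization algorithm, prior to conducting formal analyses". Then, for the primary test, "Mean OLBI scores will be compared between groups using analysis of covariance (ANCOVA), controlling for baseline severity", with the comparison made at week 8: "The primary hypothesis test (A) will be based on comparing mean outcome measures between groups at week 8". The same section states that "all analyses will be based on *intention-to-treat* principles", so all randomised participants enter the ANCOVA once their missing values are filled in.

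The section names no multiple data sets, pooling rule or variance correction. Its only sensitivity analysis adds site as a random effect, so nothing varies the handling of missing data. It does not say which variables enter the EM model, whether group is one of them, or whether random residuals are added.

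On the amount of missing data, section 5.1 gives the only figure: "Expecting a 30% dropout rate, which is common in studies of psychological interventions". Section 5.3 repeats the ANCOVA for the secondary outcomes and adds a pre-post test: "Outcomes at 6-months follow-up (pooled for both groups) will be compared to outcomes at the baseline assessment, using paired-samples t-tests".

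**The concern.** An EM algorithm estimates means and covariances. When it is used to fill in data, each missing score is replaced by a prediction, and an ordinary ANCOVA cannot tell a prediction from a measurement. Two faults can follow, depending on the imputation model.

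- **Group in the model.** The estimated difference is unbiased, but the analysis counts too many scores and sees too little residual scatter. Confidence intervals are too narrow and false positives too frequent.
- **Group not in the model.** Imputed scores show no group difference at a given baseline. The intervention effect is pulled towards zero. This weakens the test of hypothesis A and makes it easier to find the non-difference that hypothesis B predicts at week 16.

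The rule governs the primary test and every secondary test, and the planned sensitivity analysis would not reveal either fault.

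**Working it through.** **Inputs.** From the protocol: alpha 0.05, 67 evaluable per group, 30% dropout and a recruitment target of 192 (section 5.1); 1:1 allocation, hence 96 per arm (section 4). Assumed, because the protocol does not give them: a two-sided test, a moderate effect of 0.50 SD, a baseline to week-8 correlation ρ of about 0.6, and the same share m of week-8 scores missing completely at random in each arm.

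**The plan's own figure.** "we estimate that at least 67 participants are needed per group", so 134 in total; 134 / 0.70 = 191.4, rounded up to 192. This reproduces. The plan thus expects about 134 observed scores, while the ANCOVA after imputation would count 192.

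**Case 1: group in the EM model, predicted means filled in.** Let σ² be the residual variance given baseline and n = 96 the number per arm.

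- The estimate equals the one from the observed scores, so its true variance is 2σ² / [n(1 − m)].
- Imputed points add no residual scatter, so the residual variance is seen as about (1 − m)σ² and the reported variance is 2(1 − m)σ² / n.
- Reported SE / true SE = 1 − m, and type I error = 2[1 − Φ(1.96(1 − m))].
- m = 0.10: 1.96 × 0.90 = 1.764, giving 7.8%. m = 0.20: 1.568, giving 11.7%. m = 0.30: 1.372, giving 17.0%.

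In SD units at 30% missing and ρ = 0.6 (σ² = 1 − 0.36 = 0.64), the true SE is √(2 × 0.64 / 67) = 0.138 and the reported SE is about 0.70 × 0.138 = 0.097.

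**Case 2: group in the EM model, one random residual added.** The residual scatter is restored, but the added noise and the false sample size are not accounted for.

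- Reported SE / true SE = 1 / √[1/(1 − m) + m].
- m = 0.30: 1 / √(1.429 + 0.30) = 0.761; 1.96 × 0.761 = 1.491, giving 13.6%. At 20% it is 10.4% and at 10% it is 7.5%.

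**Case 3: group left out, predicted means filled in.**

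- The estimated difference is (1 − m) times the true one: 0.70 × 0.50 = 0.35 SD.
- Its true variance is (1 − m)² × 2σ² / [n(1 − m)] = 2(1 − m)σ² / n, which is what the ANCOVA reports. Type I error therefore stays at 5%.
- Coverage at a true 0.50 SD: the bias is 0.15, the SE is √(0.70 × 2 × 0.64 / 96) = 0.097, and Φ(1.96 − 0.15/0.097) is about 66%.

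**Simulation check** (96 per arm, 8,000 runs per setting, ρ from 0.3 to 0.8, 30% missing):

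| Handling | Type I error | True 0.50 SD estimated as (ρ = 0.6) |
|---|---|---|
| EM means, group included | 16.3% to 17.3% | 0.50 |
| EM plus one residual draw, group included | 13.8% to 14.7% | not run |
| EM means, group omitted | 4.3% to 5.2% | 0.35 |
| ANCOVA on observed scores only | 4.8% to 5.1% | 0.50 |

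With group included and weeks 16 and 40 observed and used to predict week 8 (all correlations 0.6), the error rate is 14.9%. If missingness depends on baseline, it is 18.2%.

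**Pre-post test of section 5.3.** For week 40 against baseline with 30% of week-40 scores filled by prediction from baseline, equal variances and ρ = 0.6, the variances below are multiples of 1/N:

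- reported: 0.70 × 2(0.4) + 0.30 × 0.4² = 0.608;
- true: 0.64 / 0.70 + 0.4² = 1.074.

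The SE ratio is √(0.608 / 1.074) = 0.752; 1.96 × 0.752 = 1.474, giving about 14%. Because the groups are pooled, leaving group out of the EM model does not protect this test.

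**The case against.** A reader might infer that the primary test has a 17% false-positive rate. The protocol does not support that as a flat statement. The figure needs group in the EM model, predictions without residual noise, and 30% of week-8 scores missing, and the protocol fixes none of the three. With group omitted there is no inflation at all; the harm is attenuation.

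Nor does the protocol say that about 58 of the 192 will lack a week-8 score. The 30% is a general dropout rate, and section 4.4 counts as dropouts those who miss four or more sessions. Group 2 has no sessions before week 8, and measures are completed online with automatic reminders, so someone who stops attending may still return the questionnaire. On the other side, section 5.1 inflates 134 to 192 as if these people supplied no outcome. This makes 30% a fair planning scenario, best shown as one point in a range.

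It can also be said that the protocol never uses the word single, and that a statistical analysis plan could specify the EM step. That is true of the detail. But the protocol does fix imputation before analysis and an ordinary ANCOVA after it. A later document that only filled in the EM settings would choose between the two faults and would not remove them.

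**Conclusion.** Wrong as written. The fault lies in a method the protocol states, not in detail it leaves open. On the natural reading, the week-8 test has either too small a standard error (type I error about 8% at 10% missing, 12% at 20%, 14% to 17% at 30%) or, if group is omitted, an effect reduced by about the missing share with the error rate near 5%. The direction of harm cannot be settled from the protocol, because it does not say what enters the EM model.

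The sizes rest on 96 per arm, data missing completely at random in equal shares, and a correlation of about 0.6. Type I error changes little over correlations from 0.3 to 0.8. The missing share matters most: with few missing week-8 scores, either fault is small.

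**What to change.** Delete the EM sentence in section 5.2. Keep the baseline-adjusted week-8 comparison as the primary test and handle missing scores in one of two ways:

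- multiple imputation with randomised group, baseline and the other OLBI and WEMWBS time points in the imputation model, then the ANCOVA in each data set, pooled by Rubin's rules; or
- a likelihood-based model of the observed post-baseline OLBI scores (weeks 8, 16 and 40) with group by time, reporting the week-8 contrast. Baseline should enter as a covariate only, so that week 0 is not both response and covariate.

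Use the same approach for the secondary ANCOVAs and the week-40 versus baseline comparisons in section 5.3.

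The cost is a change of wording, routine software and wider confidence intervals. No new data or participants are needed.
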